4.1 Study Timeline

YEAR	2010						2011			2012			2013			2014			2015			
	J	A	S	O	N	D																
Timeline – Months)																						
2010 - 2015																						
Protocol development	x																					
Submit protocol for PHE review, CDC IRB, Swazi Ethics Review	x																					
Translate study instruments	x	x																				
Recruitment and training of research staff	x	x	X	x	X	X	X															
Procurement of supplies and Swaziland laboratory preparations	x	x	X	x	X	X	X															
Data collection (Cohort A1)				x	x	x	X	x	X													
Data collection (Cross Sectional C)									x	x												
Data collection (Cohort A2)													x	x	x	X	X					
Data collection (Cohort B)													X	X	X	X	X	X				
Laboratory processing				x	x	x	X	x	x				x	x	x	x	x	X	X			
Interim analysis and progress report								x			x			x								
Data analysis																x	x	X	x	x	x	
Writing of reports																		X	x	x	x	
Dissemination & Discussion of results with stakeholders																				x	x	x

4.2 How study design meets objectives and addresses research questions

The study design incorporates two different strategies for measuring the change in seroincidence. To measure the population effect of the MC ASI campaign on HIV infection in Swaziland, we plan two independent household based samples, one prior to the campaign, one 12 months after the completion of the campaign. Each gives an

independent population “snapshot” of the current rates of infection. The second strategy enrolls a cohort of men and women in the ages at highest risk prior to the MC ASI and measures that seroincidence in this group for an additional 6-18 months after the campaign’s completion. There are several reasons for this hybrid approach. Two sequential short term cohorts provide two similar ‘snapshots’ of HIV incidence before and after the ASI campaign and coinciding with scale-up of other prevention programs. These two cohorts are representative of the national population and the HIV seroincidence estimates before and after ASI are therefore likely to represent actual changes in the epidemic. The use of a more traditional longitudinal cohort is conceptually familiar from randomized placebo controlled clinical trials; here it is used to follow HIV incidence among young adults in the highest incidence age groups over an additional 6-18 month period.

The comparison of HIV incidence rates between circumcised and uncircumcised men offers insight into the role played by MC in reducing HIV infection in the cohort and in the general population, if observed.

Blood specimens from persons identified as HIV-infected *during pre-cohort surveys* (A1 and A2) will be collected to measure viral load. These data will be used to determine the proportion of HIV infected persons with undetectable viral load in the community. The proportion of undetectable viral load at the baseline pre-cohort survey will be compared to the post-MC ASI pre-cohort survey to explore the potential effect of scale up of the ART program and viral suppression on reduced HIV incidence in the general population, if observed.

Blood specimens to measure CD4 count will be collected using a multistage clustered random sample of persons who were identified as HIV-seropositive at the pre-cohort survey for Cohort A1 (T1). These data will be used to estimate the CD4 count distribution, viral load distribution, and self-reported ART use among HIV-infected individuals at the population-level.

Surveys of sexual risk behavior and exposure to sexual risk reduction campaigns of men and women will be administered as part of the pre-cohort survey before and after the MC ASI. In addition, men and women in the longer term cohort (Cohort B) will provide sexual risk behavior information at all scheduled study visits. Repeated measures of sexual risk behaviors and exposures to sexual risk reduction campaigns over time, allows for examination of whether risk behavior changes may be coincident with MC ASI and reduced HIV incidence, if observed.

4.3 M&E Data from Programs

The ability to evaluate the stated hypotheses (Section 2.6) is predicated, in part, on achievement of the ASI targets and validity of the modeled HIV incidence reductions (Figures 1 and 2). If the ASI campaign effects a different level of MC coverage than 80%, achieves the targets in a different timeframe than one year, if the effectiveness and efficacy of MC differ, and/or if HIV incidence is increased or reduced as a result of

changes in other HIV preventative programs, then the anticipated reductions in HIV incidence—magnitude and time-horizon—will likewise be different. Knowledge of all of these factors is important, and in the 3 ½ -year context of SHIMS, awareness of MC coverage levels within specific time frames is critical.

An independent cooperative agreement was thus awarded to John Snow, Inc. to support the MOH and implementing partners in designing and implementing a real-time M&E system to keep stakeholders apprised of program performance. A hierarchical system of MC indicators is being designed, prioritized according to the time-frames within which data are needed. Not all indicators to be reported by the ASI M&E system are relevant to the SHIMS evaluation but all are presented:

Daily information

- Number of clients circumcised
 - Disaggregation
 - Service delivery team
- Number of clients with severe adverse event(s)
 - Disaggregation
 - Type of severe adverse event(s)
 - Timing /onset

Weekly information

- Weekly and cumulative number of clients circumcised
 - Disaggregation
 - Age (<1, 1-9, 10-14, 15-19, 20-24, 25-34, 35-49, 50+)
 - HIV Status (positive/documented, negative/documented, indeterminate, unknown/refused)
 - Region (1-4) of client residence
 - Urban/rural designation of client residence
 - Service delivery team
- Weekly and cumulative number of clients experiencing adverse event(s) of at least moderate severity
 - Disaggregation
 - Severity, maximum (moderate or severe)
 - Timing/onset
 - Type of adverse event
 - Service delivery team (dissemination of rates by team may be limited)
 - Surgeon (dissemination of rates by surgeon may be limited)

Monthly information

- Aggregation of all 'weekly' data to monthly
- Self-reported sexual activity by clients presenting for MC
- Number of clients provided with post-operative clinical care

- Monthly and cumulative number of persons newly diagnosed with HIV via ASI, by client self-report (regardless of whether MC surgery was performed subsequent to diagnosis)
 - Disaggregation
 - Surgical outcome (went for surgery or did not go for surgery, same day/facility)
- Monthly and cumulative number of persons provided with written referral to pre-ART services
 - Disaggregation
 - Region (1-4) of client residence
 - Urban/rural designation of client residence
 - Service delivery team
 - Pre-ART clinic on referral form

Quarterly information

- Aggregation of all 'monthly' data to quarterly
- Addition of Tinkhundla-specific residency information to regional disaggregations described above

JSI, Inc. already supports the MOH and pre-ART/ART implementing partners in the M&E system for HIV care and treatment programs. Because ART initiation may reduce the transmissibility of HIV between partners, knowledge of ART coverage levels (including any expansion resulting from ASI) is important. The MOH M&E unit presently prepares a quarterly report of treatment-related indicators, including HIV testing rates. Again, not all indicators reported by the care and treatment M&E system are relevant to the SHIMS evaluation but all are presented:

Quarterly information

- Number of persons tested for HIV
- Number of patients initiated on ART during the quarter.
- Number of patients initiated on ART since the beginning of the program (2004) by age (≥ 15 vs. < 15) and sex.
- Total number of patients currently on ART at the end of the quarter by age (≥ 15 vs. < 15) and sex.
- Number of patients currently on first-line ART at the end of the quarter by age (≥ 15 vs. < 15) and sex.
- Coverage of patients in need of ART (denominator based on most recent Spectrum projection. The numerator is "iii" above.)
- Retention on ART: Number of patients initiating ART considered still alive and on ART at 12 months. Although this is reported in each quarterly report, the retention data apply only to patients initiating ART throughout the previous year. Only by the end of the reporting year (e.g., 2009) does the quarterly report have complete

12-month cohort data for patients enrolled the previous year (e.g., 2008).
Definition of LTFU = any patient who missed a scheduled appointment by more than 60 days (this is different from PEPFAR indicators).

- Retention on first-line regimens: Number of patients initiating ART considered still alive and on first-line ART at 12 months. (Details of calculation same as “vi” above but those patients not on 1st line regimens are no longer included in the retention numerator.)
- Total number of ART patients currently enrolled who are receiving nutritional support.

Individual-level information on exposure to HIV prevention programs will be collected from all participants (Appendices E, F, N). These data, along with information collected by NERCHA on national HIV prevention mass media and community-based prevention activities will be used to evaluate the role of non-MC prevention programs during the study period.

4.4 Limitations to the study designs

The accelerated nature of the MC ASI prevents the use of evaluation designs that allow causal inference to a particular intervention such as serial rollout of different interventions or of establishment of one intervention in certain geographic areas and not others. In addition, given the overwhelming evidence of the efficacy of MC at preventing HIV acquisition among men, it would be unethical to have a true comparison group, even if that group were wait-listed for services. Instead, multiple evaluation designs and data collection on other factors that could influence HIV incidence besides an increase in MC prevalence will be used in an attempt to distinguish the effect of each of these variables on HIV incidence. For example, data on HIV-related sexual risk behaviors will be collected to determine if changes HIV incidence coincide with change in risk behaviors, resulting from the MC ASI or other ongoing HIV prevention interventions. Additionally, data on prevalence of persons on ART and proportion of persons with undetectable viral load will be collected to assist in understanding the potential effect of expanding care and treatment services on changes in HIV incidence. Cohort effects are a major threat to validity due to power reductions or bias from loss to follow-up and repeated measures (i.e. repeated counseling and interview sessions with staff reduces HIV acquisition risk among cohort participants over time). The two short term cohorts, with their one-time 6 or 12 month follow up will minimize cohort effects. The hybrid approach with addition of a longer term cohort with multiple follow-up observations will allow comparison of measurements from the different methodologies.

4.5 Prevention effectiveness/cost benefit

By combining: 1) the baseline HIV incidence rate among men; 2) the estimated HIV acquisition risk reduction (if observed) and; 3) the estimated number of males circumcised between baseline and post-MC ASI surveys, we will project and annualize the number of HIV infections averted due to MC among men in the population (as a proxy for population-level ‘impact’ of MC in men).

Via a separate study, cost-effectiveness and other economic analyses of the MC ASI will be conducted.

5.0 STUDY POPULATION

5.1 Source of household-based study population

To measure variables being evaluated and establish the baseline (Cohort A1) and post-MC ASI (Cohort A2) cohorts, pre-cohort surveys of households followed by cohort formation will take place. Separate, independent samples of enumeration areas (sampling points defined by the 2007 Swaziland Population and Housing Census), households, and individuals will be selected at baseline and post-MC ASI. The final number of households drawn, approximately 14,884 for Cohort A1 and 15,758 for Cohort A2, is derived from the sample size calculation (see Section 7.0).

Pre-cohort Survey

Prior to implementation, a representative sample of enumeration areas will be identified and an exhaustive listing of households within each sampled enumeration area will subsequently occur. A random sample of households within each enumeration area will be drawn in order to select approximately 15,000 households. All men and women, age 18-49, within sampled households may participate in the pre-cohort survey.

Formation of Cohorts

From among individuals completing the pre-cohort survey, the subset of those who are HIV-negative and who satisfy criteria for inclusion in the male and female longitudinal cohorts, will be followed for 6 months (Cohort A1) and 12 months (Cohort A2). From among individuals completing follow-up in Cohort A2, the subset of those who are HIV-negative and who meet criteria for inclusion in the male and female highest risk age group longitudinal cohort, will be followed for an additional 6-18 months (Cohort B). From among individuals completing the pre-cohort survey for Cohort A1, a cluster sampled subset of those who are HIV-infected and who satisfy criteria for inclusion/exclusion in Cross-Sectional Cohort C, will be recruited to participate in a cross-sectional observational survey (Cross-Sectional Cohort C).

5.2 Case Definitions

The following case definitions will be used throughout the study to establish participant study eligibility and outcomes.

5.2.1 HIV status

During each contact with participants, consenting adults will be tested for HIV for this study using a serial algorithm for rapid tests approved by the Swaziland National Reference Laboratory. This algorithm includes the use of the 4th generation Determine rapid test kits that are capable of detecting HIV antigens. Samples from persons that are

HIV antigen reactive will subsequently be tested using both enzyme immunoassay (EIA) and nucleic acid detection tests (NAT) in the laboratory (Appendix A). NAT are HIV-discriminatory assays approved by the FDA to detect HIV-1 protein/antigens, which are produced by the body prior to the production of antibodies. NAT will be used in this protocol to identify people who were very recently HIV-infected who might not have had their HIV infection detected if only rapid HIV tests that detect antibodies were being used. The use of HIV antigen detection tests is to avoid enrollment of acutely HIV-infected individuals into the cohorts.

1. Confirmed HIV-negative: Negative per the serial algorithm for rapid HIV testing that includes 4th generation Determine, approved for this study. See Appendix A.
2. Confirmed HIV-positive: Positive per the serial algorithm for rapid HIV testing that includes 4th generation Determine, approved for this study. See Appendix A.

Sub-categories defining duration of HIV infection among confirmed HIV-positive persons are as follows:

- HIV-positive Incident Infection: identified by direct observation of HIV seroconversion during the period of participation in the cohort, i.e. a person was confirmed HIV-negative at cohort enrollment and confirmed HIV-positive at cohort follow-up.
 - HIV-positive Non-recent/Prevalent Infection: identified as HIV-positive as part of the pre-cohort survey based upon the serial algorithm for rapid testing approved for this study. See Appendix A.
3. HIV indeterminate: Indeterminate per the serial algorithm for rapid HIV testing that includes 4th generation Determine, approved for this study. See Appendix A.

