5.3.2 Short-term Longitudinal cohorts (Cohorts A1 and A2)

- Inclusion criteria
 - Meets eligibility criteria for pre-cohort survey (listed above)
 - Confirmed HIV-negative by Swazi rapid HIV test algorithm
 - Willing to adhere and undergo all study visits and procedures
 - Able to provide answers to the study questionnaires administered in either English or siSwati
 - Able to provide consent in either English or siSwati
- Exclusion criteria
 - Stated intent to leave Swaziland indefinitely for work or any other reason in the next 6 months (baseline cohort, Cohort A1) or 12 months (post-MC ASI cohort, Cohort A2)

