6.2.4.1 Additional Study procedures for participants who test HIV-positive at the follow-up visit

- Interviewer administered questions to assess whether the participant has previously tested HIV-positive and whether HIV care and treatment has been sought.
- Counseling about the benefits of HIV care and treatment services and provision of information to help them link to these services.
- Counseling regarding importance of HIV testing of partners and referral to HIV testing sites.
- Male participants identified as newly circumcised **and** newly HIV-infected at follow-up (were uncircumcised at cohort enrollment) will be asked to provide information about the date and location of the MC surgery, whether they had an HIV test the day of the MC surgery, and the HIV test result, to help determine HIV status at the time of circumcision. Their medical records related to their MC surgery will be abstracted at the facility that performed the MC surgery to determine whether an HIV test was conducted pre-operatively and the results of the test, if done.

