6.7.2 Testing

Rapid testing

Rapid testing will be done in the home following the serial algorithm for rapid HIV testing that includes 4th generation Determine, approved for this study. See Appendix A.

Viral load measurement

Viral load measurement will be done on all plasma samples from individuals who test HIV-positive during rapid testing in the home or by EIA in the lab at the time of the pre-cohort surveys. It will also be conducted among Cross sectional Cohort C participants who consent to have their blood specimen stored for future research. Specific details regarding the type of HIV viral load assays that will be used in this study are outlined in the Laboratory Standard Operating Procedures (SOPs).

EIA/NAT testing

All plasma samples from individuals with indeterminate HIV-test results will be tested within 7 days from the time that the sample was collected with an EIA or NAT according to the rapid HIV testing algorithm approved for this study by the NRL (Appendix A). Specific details regarding the type of assays that will be used in this study are outlined in the Laboratory Standard Operating Procedures (SOPs)

All participants with an indeterminate HIV status based upon EIA/NAT testing in the laboratory will receive repeat home-based rapid HIV testing within 6 weeks (see 6.1.2.3.).

CD4 count

CD4 enumeration will be done on blood samples from Cross-Sectional Cohort C participants. Specific details regarding the type of CD4 count assays that will be used in this study are outlined in the Laboratory Standard Operating Procedures (SOPs).

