6.7.3 Quality assurance and quality control for laboratory testing

Good laboratory practices will be followed for all laboratory testing. Standard operating procedures will be used for all test and Quality Control procedures. Procedures will be in place for performing and documenting the quality of a specimen, including storage and transport conditions, monitoring of equipment and temperatures, and function indicators. At the Swazi laboratory, additional storage facilities consisting of refrigerators (4°C), freezers (-20°C), and ultra freezers (-70°C) will be available for the short term and long term storage of specimens. An effective QA/QC system will be maintained to ensure integrity of the specimens will be in place at the laboratory site. Each stored specimen will have a unique identifier which is unlinked from the study participant's name. The specimens will be stored for ten years.

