The sample size for the men’s Cohort A1 is 5,823 and for Cohort A2 is 6,165. Each person enrolled in Cohort A1 contributes 6 months of follow-up and in Cohort A2, each contributes 12 months of follow-up. The sample size is chosen to achieve sufficient “effective” person years to achieve 80% power to detect a 45% reduction in ratio of infection rates, assuming a Poisson distribution in each cohort of number of seroconversion events in total accumulated person years.

Note: Very similar sample sizes result from comparison of binomial probabilities of the proportion of the cohort infected in the pre vs. post MC ASI cohorts, provided exact methods are used. Poisson analysis is planned to accommodate varying lengths of follow-up time in the follow-up cohort.

- Men. The total number of person-years required to detect a 45% reduction in the HIV incidence rate from 2.0 per 100 person years (approximated baseline rate) to 1.1 per 100 person years (post-intervention) with a 1:2 ratio of person years in the two cohorts is 6,288. With a design effect of 1.25 and loss to follow-up of 10% and 15% in the pre- and post-MC ASI this yields a sample size of 5,823 men followed for 6 months and 6,165 men followed for 12 months in Cohort A1 and Cohort A2 respectively. (See Tables 1 and 2)

Table 1:

Effective person years required to detect 30-60% difference between infection rates with 6 month follow-up in Cohort A1, 12 month follow-up in Cohort A2, for two sided alpha of 0.05, and 80% power. Wald test statistic for slope in Poisson Regression, under assumption of simple random sample.				
λ_1	λ_2	Ratio λ_2/λ_1	Total Effective ¹ Person Years (Both serocohorts combined)	
0.0200	0.0140	0.70	15865	
0.0200	0.0130	0.65	11224	
0.0200	0.0120	0.60	8272	
0.0200	0.0110	0.55	6289	
0.0200	0.0100	0.50	4901	
0.0200	0.0090	0.45	3898	
0.0200	0.0080	0.40	3155	
0.0300	0.0210	0.70	10577	
0.0300	0.0195	0.65	7483	
0.0300	0.0180	0.60	5514	
0.0300	0.0165	0.55	4192	
0.0300	0.0150	0.50	3267	
0.0300	0.0135	0.45	2599	
0.0300	0.0120	0.40	2103	

¹Effective person years assume a simple random sample.

Number of households

The number of households required to achieve the effective sample size is shown in Table 2. The derivation of each of the adjustment factors is as follows:

- Design Effect: Design effect for HIV in men ages 15-49 of 1.25, and the DEFT of 1.32, are both based on the 2006-07 DHS.
- Household adjustment:

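### Incident infection is defined by a negative-then-positive algorithm pair with no stated confirmation; with 6 months in A1 and 12 in A2, each false case adds twice as much to the A1 rate and can produce a spurious fall

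*Protocol*

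**What the plan says.** Section 5.2 states that its case definitions govern both eligibility and outcomes. Under Section 5.2.1 an incident infection means that "a person was confirmed HIV-negative at cohort enrollment and confirmed HIV-positive at cohort follow-up". The positive state is itself an algorithm result: "Confirmed HIV-positive: Positive per the serial algorithm for rapid HIV testing that includes 4th generation Determine, approved for this study". The negative state is defined in the same way, and Section 5.3.2 makes it the entry criterion: "Confirmed HIV-negative by Swazi rapid HIV test algorithm".

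Laboratory EIA/NAT is described for antigen-reactive samples (5.2.1) and for indeterminate ones (6.1.2.3 and 6.7.2: "All plasma samples from individuals with indeterminate HIV-test results will be tested within 7 days"). Section 6.6.1 records HIV testing history, earlier results and current HIV treatment at the pre-cohort survey. Section 6.2.4.1 asks those who are positive at follow-up "whether the participant has previously tested HIV-positive and whether HIV care and treatment has been sought". No rule says what happens to the endpoint if the answer is yes.

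On follow-up, Section 7.2 says: "Each person enrolled in Cohort A1 contributes 6 months of follow-up and in Cohort A2, each contributes 12 months of follow-up". Section 8.1.3 computes the rate as seroconversions over person-years, weighted, and compares A1 with A2 by a Wald test from a Poisson regression. The sensitivity analyses there cover household clustering and demographic change.

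**The concern.** Two kinds of error turn a person into a false seroconverter: an established infection missed at enrolment, and a false positive at follow-up. Both occur once per person tested and do not grow with time at risk. Dividing the same number of false cases by half a person-year in A1 and a whole one in A2 inflates the earlier rate twice as much. If the error is equal in both surveys and true incidence is unchanged, the comparison for Primary Objectives 1a and 1b leans towards the decline that Hypotheses 1 and 2 predict. The two absolute rates, which are primary estimands in their own right, are inflated whatever the true ratio.

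On the text shown, someone who tells the interviewer of a positive test or ART before enrolment would still be counted as newly infected.

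**Working it through.** **The plan's own figures first.** For men, rates 2.0 and 1.1 per 100 person-years (PY), person-years split 1:2, two-sided alpha 0.05 and 80% power:

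T = (1.96 + 0.84)² × [1/(0.020/3) + 1/(2 × 0.011/3)] / (ln 0.55)² = 6,289 effective PY with unrounded normal quantiles. The protocol gives 6,288 in the text and 6,289 in Table 1. Enrolment follows: 2,096 × 1.25 / 0.5 / 0.90 = 5,822 and 4,192 × 1.25 / 0.85 = 6,165 (stated: 5,823 and 6,165).

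**Weight of one false case (men).** Completers: 5,823 × 0.90 = 5,241 in A1 and 6,165 × 0.85 = 5,240 in A2. Person-years: 2,620 and 5,240. One false case adds 100/2,620 = 0.038 per 100 PY in A1 and 100/5,240 = 0.019 in A2, a factor of 2.

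**Model.** Let FN be the chance that an established infection is missed at enrolment and FP the chance of a false positive at follow-up. With prevalence p, the share of the cohort falsely counted as incident is

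m = p·FN / [(1 − p) + p·FN] + FP.

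The apparent rates are λ₁ + m/0.5 in A1 and λ₂ + m/1.0 in A2.

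Inputs from Section 7.2: p = 23% in men and 35% in women (77% and 65% uninfected); λ = 2.0 and 3.0 per 100 PY; effective PY 2,096 and 4,192 in men, 2,615 and 5,297 in women. FN and FP are assumptions. The model also assumes that every infection missed at enrolment is detected at follow-up.

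**No true change:**

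| FN / FP (assumed) | Sex | m | A1 vs A2, per 100 PY | RR | Two-sided rejection |
|---|---|---|---|---|---|
| 0.2% / 0.05% | Men | 0.110% | 2.22 vs 2.11 | 0.95 | 5.9% |
| | Women | 0.158% | 3.32 vs 3.16 | 0.95 | 6.6% |
| 0.5% / 0.1% | Men | 0.249% | 2.50 vs 2.25 | 0.90 | 9.4% |
| | Women | 0.369% | 3.74 vs 3.37 | 0.90 | 13.1% |
| 1% / 0.2% | Men | 0.498% | 3.00 vs 2.50 | 0.83 | 21% |
| | Women | 0.736% | 4.47 vs 3.74 | 0.84 | 34% |

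In the middle row, 5,241 × 0.249% = 13 false cases in men in A1, against 2,620 × 0.02 = 52 true ones.

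**Other true ratios (men, middle row).** True 0.80: (1.6 + 0.249)/(2.0 + 0.498) = 0.74. True 0.55: (1.1 + 0.249)/2.498 = 0.54. True 0.50: (1.0 + 0.249)/2.498 = 0.50, no bias. Below 0.50 the bias reverses: a true 0.40 with m = 0.2% reads (0.8 + 0.2)/(2.0 + 0.4) = 0.417, so the fall is understated. The pull is towards 0.50, the ratio of the follow-up times.

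**The case against.** A reader might infer that any rapid-negative then rapid-positive pair is taken at face value, that nobody ever checks it, and that a false fall is therefore built into the design. The document does not support that.

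- The algorithm is serial and includes a fourth-generation test, and antigen-reactive and indeterminate samples go to EIA/NAT. Appendix A, which holds the algorithm, is not shown, and laboratory detail sits in SOPs. All that can be said is that the text shown contains no confirmation step.
- No sensitivity or specificity is given. At m = 0.05% to 0.1% in men, the ratio under no change is 0.976 to 0.955 and the rejection probability 5.2% to 5.8%, which is negligible. False negatives that recur in the same person would not be counted at all.
- The false fall needs a true ratio above 0.50 and nearly vanishes at the effect the study is powered for.
- Infections in the early window missed at enrolment are largely offset by those missed at follow-up, so they are not part of this bias.
- Section 6.2.4 requires identity to be verified at follow-up, which limits mix-ups.
- Section 6.7.3 says of stored specimens: "The specimens will be stored for ten years". It does not say that plasma from HIV-negative A1 and A2 participants is kept, or that re-testing it is permitted.

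These points stand and limit the size and certainty of the claim. They do not remove the gap. Section 5.2.1 fixes the outcome definition, and no rule uses the interview answers. The special questionnaire, record review and assays in Section 8.9 concern men who became both circumcised and infected. A misclassification sensitivity analysis could properly sit in a SAP; the endpoint definition is already set here.

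One further caution bears on the remedy. Applying NAT only to seroconverters' enrolment plasma would remove window-period cases at entry while those missed at follow-up stay uncounted. With w the extra window in years, the ratio under no change becomes (1 − w)/(1 − w/0.5). For an assumed 7, 14 or 21 days this is 1.02, 1.04 or 1.07, an upward bias that would hide part of a decline.

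**Conclusion.** The point holds in a conditional form. The stated endpoint leaves established infections missed at enrolment and follow-up false positives in the count, and unequal follow-up doubles their weight in A1. Both absolute rates are inflated at any non-zero error.

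The effect on the ratio depends on the truth. With no change, it reads about 0.95 to 0.83 over the assumed error range; at 0.55, about 0.54; at 0.50, there is no shift. The bias therefore matters most where the true effect is null or modest, which is where a false claim of decline would mislead. These figures assume equal error rates in both surveys and detection at follow-up of every infection missed at enrolment; the error rates themselves are not in the protocol. The change is worth making because its main part needs no new data.

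**What to change.** Amend Section 5.2.1 as follows.

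1. Do not count an apparent seroconversion as incident without adjudication when the pre-cohort or follow-up interview reports a positive test or ART before enrolment. If the evidence supports it, reclassify the person as prevalent at enrolment and remove them from the cohort. This uses only data already collected.
2. Where plasma from both visits is available and its use is permitted, confirm apparent seroconverters by EIA at both visits to the same detection standard. Reclassify enrolment-reactive cases as prevalent and unconfirmed follow-up cases as negative. Do not exclude on NAT reactivity alone at enrolment.
3. Report the A1 versus A2 rate ratio with and without the reclassified cases.

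Cost: wording, an adjudication step, and laboratory work on about 340 to 450 apparent seroconverters. At the protocol's rates these are 52 men and 98 women in A1, plus 58 to 105 men and 129 to 199 women in A2, depending on the true reduction: 52 + 98 + 58 + 129 = 337 and 52 + 98 + 105 + 199 = 454. The downside is slightly fewer counted events and so somewhat lower power.
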